5.3.2.2. Supplementary Estimand 1 (Hypothetical)

a. Study intervention:

- Guselkumab (experimental treatment/intervention) in addition to standard-of-care
- Placebo in addition to standard-of-care

b. **Population:** Participants between 18 and 75 with active LN (defined by meeting the classification criteria for SLE by the 2019 European League Against Rheumatism (EULAR)/ACR, having a Class III-IV kidney biopsy documentation of ISN/RPS proliferative nephritis within the last 6 months prior to or during screening despite receiving one or more standard-of-care treatments.

c. **Variable:** Responder binary variable, defined as a participant achieving at least 50% decrease in proteinuria from baseline at Week 24

d. **Summary measure (Population-level summary):** Difference in proportion between the study interventions

e. Intercurrent events and their corresponding strategies:

Intercurrent Events	Strategy for Addressing Intercurrent Events and Its Description
Discontinuation (DC) of study intervention for any reason excluding COVID-19 related discontinuations	Hypothetical strategy: The intercurrent event is addressed with a hypothetical strategy, as if these intercurrent events would not have occurred.
Medication Intercurrent Event	Hypothetical Strategy: Same as above

 1. Exceeding baseline glucocorticoid dose 2. Increase above 10 mg/d prednisone equivalent after Week 12, use of new or increased dose of concomitant medication related to LN or other immunosuppressive agents, within 8 weeks prior to the endpoint 3. Initiation of prohibited medications at any time prior to the endpoint 
Note: adjustments in glucocorticoids are permitted up to and including Week 12. Nonsystemic glucocorticoids, NSAIDs, antimalarials and topical agents will not be considered an intercurrent event.
	
	
Note: Data after the intercurrent event will not be utilized in the analysis

Difference from Primary Estimand: The strategy to address the intercurrent events is to assume that participants with this intercurrent event is considered to have missing data at and after the event occurred instead of not having achieved at least 50% decrease in proteinuria after this event as in the primary estimand.

5.3.2.3. Supplementary Estimand 2 (Treatment Policy (de Facto))

a. Study intervention:

- Guselkumab (experimental treatment/intervention) in addition to standard-of-care
- Placebo in addition to standard-of-care

b. Population: Participants between 18 and 75 with active LN (defined by meeting the classification criteria for SLE by the 2019 European League Against Rheumatism (EULAR)/ACR, having a Class III-IV kidney biopsy documentation of ISN/RPS proliferative nephritis within the last 6 months prior to or during screening despite receiving one or more standard-of-care treatments.

c. Variable: Responder binary variable, defined as a participant achieving at least 50% decrease in proteinuria from baseline at Week 24

d. Summary measure (Population-level summary): Difference in proportion between the study interventions

e. Intercurrent events and their corresponding strategies:

Intercurrent Events	Strategy for Addressing Intercurrent Events and Its Description
---------------------	---

Discontinuation (DC) of study intervention for any reason excluding COVID-19 related discontinuations	Treatment Policy Strategy: The intercurrent event addressed with a treatment policy strategy, targeting the effect of the assignment to the treatment group, regardless of the occurrence of the intercurrent events.
Medication Intercurrent Event 1. Exceeding baseline glucocorticoid dose 2. Increase above 10 mg/d prednisone equivalent after Week 12, use of new or increased dose of concomitant medication related to LN or other immunosuppressive agents, within 8 weeks prior to the endpoint 3. Initiation of prohibited medications at any time prior to the endpoint Note: adjustments in glucocorticoids are permitted up to and including Week 12. Nonsystemic glucocorticoids, NSAIDs, antimalarials and topical agents will not be considered an intercurrent event.	Treatment Policy Strategy: Same as above
	Note: Under the Treatment Policy strategy, all data are utilized/used, regardless of the occurrence of an intercurrent event.

Difference from Primary Estimand: The strategy to address the intercurrent events is that the intercurrent events do not affect the outcome, and the data collected at and after the event will be used for analysis, instead of assuming participants have not achieved at least 50% decrease in proteinuria after the event as in the primary estimand.

5.3.2.4. Supplementary Estimand 3 (Composite)

a. Study intervention:

- Guselkumab (experimental treatment/intervention) in addition to standard-of-care
- Placebo in addition to standard-of-care

b. **Population:** Participants between 18 and 75 with active LN (defined by meeting the classification criteria for SLE by the 2019 European League Against Rheumatism (EULAR)/ACR, having a Class III or IV predominant kidney biopsy documentation of ISN/RPS proliferative nephritis within the last 6 months prior to or during screening despite receiving one or more standard-of-care treatments.

c. **Variable:** Responder binary variable, defined as a participant achieving at least 50% decrease in proteinuria from baseline at Week 24 who does not:

- discontinue study intervention for any reason excluding COVID-19 related discontinuations or
- meet the Medication Intercurrent Event in Section (e) below

d. **Summary measure (Population-level summary):** Difference in proportion between the study interventions

e. Intercurrent events and their corresponding strategies:

Intercurrent Events	Strategy for Addressing Intercurrent Events and Its Description
Discontinuation (DC) of study intervention for worsening of LN	Composite Strategy: A participant with this intercurrent event is considered to not have achieved at least 50% decrease in proteinuria after this event, the occurrence of this intercurrent event being captured in the variable definition.
Medication Intercurrent Event 
 1. Exceeding baseline glucocorticoid dose 2. Increase above 10 mg/d prednisone equivalent after Week 12, use of new or increased dose of concomitant medication related to LN or other immunosuppressive agents, within 8 weeks prior to the endpoint 3. Initiation of prohibited medications at any time prior to the endpoint 
Note: adjustments in glucocorticoids are permitted up to and including Week 12. Nonsystemic glucocorticoids, NSAIDs, antimalarials and topical agents will not be considered an intercurrent event.
	Composite Strategy: Same as above

Difference from Primary Estimand: The intercurrent event “discontinuation of study intervention for any reason” is changed to “discontinuation of study intervention for worsening of LN”.

5.3.2.5. Supplementary Estimand 4 (Composite)**a. Study intervention:**

- Guselkumab (experimental treatment/intervention) in addition to standard-of-care
- Placebo in addition to standard-of-care

b. Population: Participants between 18 and 75 with active LN (defined by meeting the classification criteria for SLE by the 2019 European League Against Rheumatism (EULAR)/ACR, having a Class III or IV predominant kidney biopsy documentation of ISN/RPS proliferative nephritis within the last 6 months prior to or during screening despite receiving one or more standard-of-care treatments.

c. Variable: Responder binary variable, defined as a participant achieving at least 50% decrease in proteinuria from baseline at Week 24 who does not:

- discontinue study intervention for any reason or
- meet the Medication Intercurrent Event in Section (e) below

d. **Summary measure (Population-level summary):** Difference in proportion between the study interventions

e. **Intercurrent events and their corresponding strategies:**

Intercurrent Events	Strategy for Addressing Intercurrent Events and Its Description
Discontinuation (DC) of study intervention for any reason excluding COVID-19 related discontinuations	Composite Strategy: A participant with this intercurrent event is considered to not have achieved at least 50% decrease in proteinuria after this event, the occurrence of this intercurrent event being captured in the variable definition.

Medication Intercurrent Event
 
 1. Exceeding baseline glucocorticoid dose 2. Increase above 10 mg/d prednisone equivalent after Week 12, use of new or increased dose of concomitant medication related to LN or other immunosuppressive agents, within 8 weeks prior to the endpoint 3. Initiation of prohibited medications at any time prior to the endpoint 
Note: adjustments in glucocorticoids are permitted up to and including Week 12. Nonsystemic glucocorticoids, NSAIDs, antimalarials and topical agents will not be considered an intercurrent event.
	Composite Strategy: Same as above
Discontinued study intervention due to COVID-19 related reasons	
Hypothetical strategy: The intercurrent event is addressed with a hypothetical strategy, as if these intercurrent events would not have occurred.
 
Note: Data after the intercurrent event will not be utilized in the analysis

Difference from Primary Estimand: For discontinuations due to COVID-19 related event or situations, the participant's data after the event will not be used after the intercurrent event.

5.3.2.6. Supplementary Estimand 5 (Composite)

a. **Study intervention:**

- Guselkumab (experimental treatment/intervention) in addition to standard-of-care
- Placebo in addition to standard-of-care

b. **Population:** Participants between 18 and 75 with active LN (defined by meeting the classification criteria for SLE by the 2019 European League Against Rheumatism (EULAR)/ACR, having a Class III or IV predominant kidney biopsy documentation of

ISN/RPS proliferative nephritis within the last 6 months prior to or during screening despite receiving one or more standard-of-care treatments.

- c. **Variable:** Responder binary variable, defined as a participant achieving at least 50% decrease in proteinuria from baseline at Week 24 who does not:
- discontinue study intervention for any reason excluding COVID-19 related discontinuations or
 - meet the Medication Intercurrent Event in Section (e) below
- d. **Summary measure (Population-level summary):** Difference in proportion between the study interventions
- e. **Intercurrent events and their corresponding strategies:**

Intercurrent Events	Strategy for Addressing Intercurrent Events and Its Description
Discontinuation (DC) of study intervention for any reason excluding COVID-19 related discontinuations	Composite Strategy: A participant with this intercurrent event is considered to not have achieved at least 50% decrease in proteinuria after this event, the occurrence of this intercurrent event being captured in the variable definition.
Medication Intercurrent Event 
 1. Exceeding baseline glucocorticoid dose 2. Increase above 10 mg/d prednisone equivalent after Week 12, use of new or increased dose of concomitant medication related to LN or other immunosuppressive agents 3. Initiation of prohibited medications at any time prior to the endpoint 
Note: adjustments in glucocorticoids are permitted up to and including Week 12. Nonsystemic glucocorticoids, NSAIDs, antimalarials and topical agents will not be considered an intercurrent event.
	Composite Strategy: Same as above

4. **Difference from Primary Estimand:** The first Medication Intercurrent Event, “Increase above 10 mg/d prednisone equivalent, use of new or increased dose of concomitant medication related to LN or other immunosuppressive agents” can occur at any time after Week 12, not just within 8 weeks prior to the endpoint.

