Antimalarials (chloroquine, hydroxychloroquine, or quinacrine)	≤ 250 mg/day chloroquine (≤ 3 mg/kg/day) ≤ 400 mg/day hydroxychloroquine ≤ 100 mg/day quinacrine	Stable dosing through Week 52. Initiation of new antimalarial treatment is not permitted through Week 52.
Oral glucocorticoids ^b	Stable oral glucocorticoids at minimum prednisone equivalent dose of 10 mg/day and maximum 1 mg/kg/day or ≤ 60 mg/day, whichever is lower.	Week 2 Through Week 12 - tapering starting from Week 2 to prednisone 5 mg equivalent PO daily by Week 12 according to schedule (Appendix 7 [Section 10.7]) Reason(s) for not tapering glucocorticoids should be documented
NSAIDs and other analgesics	Stable dosing through Week 52 with no more than the usual marketed doses approved in the country where the study is being conducted. Notable changes in NSAID dosing to be recorded in concomitant medications. The initiation of treatment with NSAIDs should be avoided unless other analgesics are contraindicated.	
Anti-hypertensive medications (ARBs or ACE inhibitors)	No more than the usual marketed doses approved in the country where the study is being conducted. The initiation of treatment with ARB or ACE inhibitors should be avoided between randomization and Week 52 unless other hypertensive treatments are contraindicated. Substitution of ACE inhibitors for ARBs or ARBs for ACE inhibitors is permitted if medically necessary.	
Non-biologic immunomodulators: MMF MPA	≤ 3 g/day ≤ 2.2 g/day	Stable dosing through Week 52. Initiation of a new immunomodulator is not permitted through Week 52.

^a Permitted concomitant medications are not supplied by the sponsor.

^b Between Weeks 12 and 52, participants requiring average daily doses of glucocorticoids for SLE or LN disease activity that exceed their baseline dose at Week 0 may be categorized as TFs. While these participants will be permitted to remain in the study, the investigator must consider whether glucocorticoid dose increases to an average daily dose ≥ 60 mg prednisone or equivalent for more than 7 consecutive days or whether a requirement for multiple rescues with glucocorticoid therapy between Weeks 12 and 52 should result in discontinuation of study intervention administration (see Section 7.1).

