6.5.2. Glucocorticoid Therapy

Participants likely to require multiple courses of systemic glucocorticoids for reasons other than SLE or LN (eg, history of uncontrolled asthma, uncontrolled chronic obstructive pulmonary disease, etc) should be excluded from study participation, including the LTE. However, participants may receive short courses (10 days or less) of oral glucocorticoids for reasons such as prophylactic therapy before surgery (stress-dose glucocorticoids), therapy for certain infections, acute exacerbation of asthma or chronic obstructive pulmonary disease, or other condition (eg, contact dermatitis) not related to increased SLE or LN disease activity. Dosage, duration, and reason for glucocorticoid use in these instances must be documented.

Unnecessary changes in glucocorticoid dose are discouraged, and any dose adjustments are recommended to be made in small amounts. Changes in glucocorticoid dosing other than those described in this section of the protocol are allowed only for medical necessity. The degree and timing of any unspecified glucocorticoid adjustments should be carefully considered as this may have a significant impact on the study results and upon continuation of study intervention.

Oral Glucocorticoids

Participants must be receiving this medication at screening and be on a stable dose equivalent to an average daily dose of 1 mg/kg/day or ≤ 60 mg/day prednisone (or equivalent), whichever is lower for at least 2 weeks prior to the first study intervention dose. Participants are required to be receiving at least 10 mg/day prednisone equivalent at screening and randomization.

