5.4.2.1.5. Time to Treatment Failure (TF)

Time to TF is defined as time to the first occurrence of TF from baseline. TF is defined as the intercurrent events for the Supplementary Composite Estimand 5 of the primary endpoint in Section 5.3.2.6.

5.4.2.2. Estimand(s)**5.4.2.2.1. Proportion of Participants Achieving Complete Renal Response (CRR) at Week 24****Composite Estimand****1. Study intervention:**

- Guselkumab (experimental treatment/intervention) in addition to standard-of-care
- Placebo in addition to standard-of-care

2. Population: Participants between 18 and 75 with active LN (defined by meeting the classification criteria for SLE by the 2019 European League Against Rheumatism (EULAR)/ACR, having a Class III-IV kidney biopsy documentation of ISN/RPS proliferative nephritis within the last 6 months prior to or during screening despite receiving one or more standard-of-care treatments.

3. Variable: Responder binary variable, defined as a participant achieving Complete Renal Response (CRR) at Week 24 who does not:

- discontinue study intervention for any reason excluding COVID-19 related discontinuations or
- meet the Medication Intercurrent Event in Section (5) below

4. Summary measure (Population-level summary): Difference in proportion between the study interventions

5. Intercurrent events and their corresponding strategies:

Intercurrent Events	Strategy for Addressing Intercurrent Events and Its Description
Discontinuation (DC) of study intervention for any reason excluding COVID-19 related discontinuations	Composite Strategy: A participant with this intercurrent event is considered to not have achieved CRR after this event, the occurrence of this intercurrent event being captured in the variable definition.
Medication Intercurrent Event 
 1. Exceeding baseline glucocorticoid dose 2. Increase above 10 mg/d prednisone equivalent after Week 12, use of new or increased dose of concomitant medication related to LN or other immunosuppressive agents, within 8 weeks prior to the endpoint 3. Initiation of prohibited medications at any time prior to the endpoint 
Note: adjustments in glucocorticoids are permitted up to and including Week 12. Nonsystemic glucocorticoids, NSAIDs, antimalarials and topical agents will not be considered an intercurrent event.
	Composite Strategy: Same as above

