Medication Intercurrent Event 
 1. Exceeding baseline glucocorticoid dose 2. Increase above 10 mg/d prednisone equivalent after Week 12, use of new or increased dose of concomitant medication related to LN or other immunosuppressive agents, within 8 weeks prior to the endpoint 3. Initiation of prohibited medications at any time prior to the endpoint 
Note: adjustments in glucocorticoids are permitted up to and including Week 12. Nonsystemic glucocorticoids, NSAIDs, antimalarials and topical agents will not be considered an intercurrent event.
	Composite Strategy: Same as above
Sustained increase of prednisone equivalent between Week 24 and Week 44 is allowed up to 40 mg/d for ≤10 days once for non-SLE/LN treatment (eg, COPD, asthma, contact dermatitis).	Treatment Policy Strategy: The intercurrent event addressed with a treatment policy strategy, targeting the effect of the assignment to the treatment group, regardless of the occurrence of the intercurrent events.
	Note: Under the Treatment Policy strategy, all data are utilized/used, regardless of the occurrence of an intercurrent event.

5.4.2.2.3.2. Supplementary Estimand

All attributes (1-4) of the supplementary estimand are the same as above main estimand (Section 5.4.2.2.3.1) except for the intercurrent events, where the treatment policy strategy is omitted.

5. Intercurrent events and their corresponding strategies:

Intercurrent Events	Strategy for Addressing Intercurrent Events and Its Description
Discontinuation (DC) of study intervention for any reason excluding COVID-19 related discontinuations	Composite Strategy: A participant with this intercurrent event is considered to not have achieved 50% decrease in proteinuria after this event, the occurrence of this intercurrent event being captured in the variable definition.
Medication Intercurrent Event 
 1. Exceeding baseline glucocorticoid dose 2. Increase above 10 mg/d prednisone equivalent after Week 12, use of new or increased dose of concomitant medication related to LN or other immunosuppressive agents within 8 weeks prior to the endpoint 3. Initiation of prohibited medications at any time prior to the endpoint 
Note: adjustments in glucocorticoids are permitted up to and including Week 12. Nonsystemic glucocorticoids, NSAIDs, antimalarials and topical agents will not be considered an intercurrent event.
	Composite Strategy: Same as above

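### Time to treatment failure counts a short non-lupus steroid course above the baseline dose in Weeks 24–44, which the SAP's Week 52 and time-to-CRR main estimands disregard

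*SAP*

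**What the plan says.** **TF definition.** SAP 5.4.2.1.5 states: "TF is defined as the intercurrent events for the Supplementary Composite Estimand 5 of the primary endpoint in Section 5.3.2.6". Supplementary Estimand 5 has two steroid triggers. Item 1 is any dose above baseline. Item 2 begins "Increase above 10 mg/d prednisone equivalent after Week 12, use of new or increased dose of concomitant medication related to LN" and, unlike in the primary estimand, applies at any time after Week 12. A note allows steroid adjustments through Week 12 and exempts nonsystemic steroids, NSAIDs, antimalarials and topical agents. Nothing exempts a systemic course by its reason or length. SAP 5.4.2.2.8 lists no intercurrent events for time to TF, so it adds no exemption. SAP 5.4 keeps the endpoint in the CSR, on the FAS.

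**Other main estimands.** SAP 5.4.2.2.3.1 (Week 52 proteinuria), 5.4.2.2.4.1 (Week 52 CRR) and 5.4.2.2.7.1 (time to CRR) each carry an extra row: "Sustained increase of prednisone equivalent between Week 24 and Week 44 is allowed up to 40 mg/d". The row is limited to 10 days or less, once, for a non-SLE/LN reason, and is handled by treatment policy. SAP 5.4 keeps these endpoints in the CSR too.

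**Protocol.** Section 6.5.2 says "participants may receive short courses (10 days or less) of oral glucocorticoids for reasons such as prophylactic therapy before surgery", certain infections, asthma or COPD exacerbations, and other conditions "not related to increased SLE or LN disease activity". Table 6 footnote b says that, between Weeks 12 and 52, "participants requiring average daily doses of glucocorticoids for SLE or LN disease activity that exceed their baseline dose" may be categorized as TFs. A bullet in Section 6.5.2 makes any increase above 10 mg/day after Week 12 a TF, with no reason attached.

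**The concern.** Time to TF should measure failure of lupus treatment. As written, an asthma flare or infection treated with a short permitted steroid course can be a TF event, while other endpoints in the same report disregard that course because it was not for lupus. If such courses are equally common in both arms, they add the same hazard to each and draw the hazard ratio towards 1. If they differ by arm, for example through steroid-treated infections, the ratio is biased in the direction of the difference. A likely cause is that the TF definition was borrowed from a Week 24 estimand, where an exemption for Weeks 24–44 has no role, and then used for a time-to-event endpoint that is not cut at Week 24.

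**Working it through.** **1. Trace one course.** Take 30 mg/d for 7 days at Week 30, for asthma. Compare a baseline of 10 mg/d (the protocol minimum) with one of 40 mg/d.

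| Rule | Baseline 10 mg/d | Baseline 40 mg/d |
|---|---|---|
| Week 52, item 1 (above baseline, no time window) | Met | Not met |
| Week 52, item 2 (only the 8 weeks before the endpoint, Weeks 44–52) | Outside window | Outside window |
| Week 52 exemption row | Applies; course disregarded | Not needed |
| TF, item 1 | Met | Not met |
| TF, item 2 (any time after Week 12) | Met | Met |
| Time to TF | Event at Week 30 | Event at Week 30 |

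The endpoints differ in both columns. Only in the first does the steroid's reason decide it: the same course given for lupus would fail Week 52 through item 1. In the second column, the 8-week window alone makes the difference. The conflict over reason is therefore confined to courses above baseline, up to 40 mg/d, 10 days or less, once, in Weeks 24–44.

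The SAP confirms this reading. Its supplementary estimands that drop the exemption row (5.4.2.2.3.2, 5.4.2.2.4.2, 5.4.2.2.7.3) say that a participant with such a course then cannot be a responder afterwards. Without the row, the steroid items catch non-lupus courses, and the TF definition has no such row.

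**2. Size.** The plan gives no figure to reproduce. All inputs below are assumptions: placebo lupus TF 40% by Week 24, true HR 0.5, constant hazards, and a share c of each arm with one course by Week 24.

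- Cumulative lupus TF hazard to Week 24: placebo −ln(0.6) = 0.5108; guselkumab 0.5 × 0.5108 = 0.2554.
- Added hazard m = −ln(1 − c): 0.0513, 0.1054 and 0.1625 for c = 5%, 10% and 15%.

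Courses counted from Week 0, HR = (0.2554 + m)/(0.5108 + m):
- 5%: 0.3067/0.5621 = 0.55
- 10%: 0.3608/0.6162 = 0.59
- 15%: 0.4179/0.6733 = 0.62

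The TF definition permits adjustments through Week 12, so only m/2 should count. The ratio of cumulative hazards is then:
- 5%: 0.2811/0.5364 = 0.52
- 10%: 0.3081/0.5635 = 0.55
- 15%: 0.3367/0.5921 = 0.57

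A Cox model gives more weight to the earlier period, when more participants are at risk and the ratio is still 0.5. Solving its large-sample score equation gives 0.52, 0.54 and 0.56.

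For unequal rates (10% guselkumab, 5% placebo), counting throughout gives 0.3608/0.5621 = 0.64, and counting after Week 12 only gives 0.57 from the Cox equation.

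These figures run to Week 24, whereas the conflict lies in Weeks 24–44. They show the mechanism and its order of size, not how much the fix would recover.

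**3. Against the noise.** With 30 per arm, expected events are 30 × 0.4 = 12 on placebo and 30 × (1 − √0.6) = 6.76 on guselkumab. The SE of log HR is √(1/12 + 1/6.76) = 0.481. The 80% CI around 0.5 is 0.5 × exp(±1.2816 × 0.481), or 0.27 to 0.93.

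**The case against.** The strongest reply is that the SAP follows the protocol. The unqualified bullet in protocol 6.5.2 makes any increase above 10 mg/day after Week 12 a TF, and the amendment history shows that Amendment 3 added it on purpose. The permission for short courses concerns concomitant therapy and does not mention TF scoring. Footnote b says only that participants may be categorized as TFs, and it concerns doses above baseline. This stands: a reader might infer that the SAP departs from the protocol, but the protocol itself points both ways.

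Endpoints may also use different event rules, and counting confounding steroid use as failure is a conventional conservative choice. That would answer the point if the SAP said the difference was intended. It does not, and it accepts the lupus/non-lupus distinction for three other endpoints.

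Two wider readings are tempting. One is that the SAP exempts all permitted short courses elsewhere. It does not: courses before Week 24, after Week 44, repeated, or above 40 mg/d have no exemption in those main estimands either. The other is that the Week 24 estimands have the same fault, because a course above baseline between Weeks 12 and 16 can force non-response through item 1. That follows from the text, but it contradicts nothing in the SAP. An exemption there would be a preference.

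**Conclusion.** The concern holds in a narrow form. For one kind of course (non-SLE/LN, above baseline, up to 40 mg/d, 10 days or less, once, Weeks 24–44), the SAP scores a TF event on one reported endpoint and disregards the course on three others. The direction of the effect is clear: towards 1 if the arms have equal rates, biased if they do not. The size is unknown. The range of 0.52–0.62 against a true 0.5 rests wholly on assumed rates, and its lower part (0.52–0.56) fits the TF definition better, since adjustments through Week 12 do not count. A reader might infer that the time-to-TF result would change materially. The documents do not support that: early termination leaves fewer participants followed past Week 24, and the illustrated shift is well inside the 80% interval of 0.27–0.93 even at the original 30 per arm. It is worth correcting because it is an inconsistency in scoring, cheap to remove before unblinding.

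**What to change.** In SAP 5.4.2.1.5, add the exemption row already used in 5.4.2.2.3.1, 5.4.2.2.4.1 and 5.4.2.2.7.1 to the TF definition, with all its limits unchanged and for scoring only. Do not extend it to all time after Week 12, and do not add it to the Week 24 estimands. Reconcile the row with protocol Table 6 footnote b, the short-course permission in 6.5.2 and the unqualified bullet in 6.5.2; this review takes no view on which steroid rule is right. If the sponsor intends TF to include non-lupus courses, the SAP should say so and explain why the other endpoints differ.

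The cost is SAP wording and a blinded review of concomitant steroid records before the single database lock. Protocol 6.5.2 already requires dosage, duration and reason to be documented, and 6.5 requires the indication in the eCRF. The downside is that TF scoring then depends on the recorded reason and duration of the course, so the review must be finished before unblinding.
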